### **3.3. OVERALL STUDY DESIGN**

This is a 4-week phase III, multicenter, double-masked, vehicle-controlled study to evaluate safety and efficacy of cenegermin ophthalmic solution at 20 mcg/mL solution versus vehicle, in patients with severe Sjogren's DED who are under treatment with topical Cyclosporine A (or other drugs of the same class). Patients will be evaluated as per Section 2 "SCHEDULE OF EVALUATIONS".

During the screening (day-8) all procedures for inclusion will be performed. From the day of screening the patients will stop any kind of further treatment, except CsA and commercially available preservative free artificial tears provided by Sponsor for a period of 8 days and 10 days as maximum: day -8 until the baseline visit (day 1+2); Figure 1. At the end of the wash out period (day -8 to baseline), patients meeting the entry criteria for this study will be randomized 1:1 and treated for 4 weeks with either cenegermin ophthalmic solution 20 mcg/mL TID or vehicle TID.

In addition to topical CsA eye drops (both groups will continue with topical CsA eye drops, or other topical ophthalmic treatment of the same class, as previously prescribed), during the 4 weeks of masked treatment only the administration of IMP is allowed. Nevertheless, if strictly needed, the patient can take preservative

free artificial tears (provided by the Sponsor). The use ( $n^{\circ}$  drops/day) of preservative free artificial tears will be clearly documented in a patient's diary and in the eCRF.

Eight weeks post treatment with no further topical ocular treatment except CsA and commercially available preservative-free artificial tears provided by the Sponsor TID will follow the completion of the double-blind treatment. During this follow up period, the patient can administer additional preservative-free artificial tear eye drops, provided by Sponsor, only if strictly needed, and must document in the patient's diary the number of additional drops administered for each eye.

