#### 9.3 Use of preservative free artificial tears

The use (n° drops/day) of preservative free artificial tears will be summarized with descriptive statistics by treatment group and overall, by study period (treatment / follow-up) and overall according to the following formulas:

$$Use_{TREAT} = \frac{total \ number \ of \ drops \ of \ the \ preservative \ free \ artificial \ tears \ during \ the \ treatment \ period}{total \ number \ of \ days \ of \ the \ treatment \ period} \times 100$$

$$Use_{F-UP} = \frac{total \ number \ of \ drops \ of \ the \ preservative \ free \ artificial \ tears \ during \ the \ follow - \ up \ period}{total \ number \ of \ days \ of \ the \ follow - \ up \ period} \times 100$$

Details are provided in Table 3.

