| Total number of drops in the
eligible eye scheduled during the
treatment period             | 3*(Date of End of Treatment visit – Date of Randomization + 1) – (assessments not done on Randomization visit + assessments not done on End of Treatment visit)  |
|---|--|
| The extent of exposure (days)   | Date of last administration of IMP – Date of first administration of IMP + 1   |
| Total number of drops of the
preservative free artificial tears
during the treatment period | Sum of Morning/Afternoon/Evening Number of drops taken for eligible eye between Randomization visit date and End of Treatment date.
(from the eCRF form "Frequency of preservative free artificial tears use" forms)  |
| Total number of days of the treatment period  | End of Treatment date – Randomization date + 1   |
| Total number of drops of the
preservative free artificial tears
during the follow-up period | Sum of Morning/Afternoon/Evening Number of drops taken after End of Treatment date.
(from the eCRF form "Frequency of preservative free artificial tears use" forms)  |
| Total number of days of the follow-up period  | Last follow-up available visit* date – End of Treatment date + 1
(* with assessment of Frequency of preservative free artificial tears use)   |
| Time from randomization to study discontinuation (days)   | End of Study date – Randomization date + 1   |
| Primary and Secondary Sjögren's   | For the subgroup analyses, a patient will be classified as primary Sjögren's syndrome if the patient experienced any previous and/or concomitant ocular with diagnosis='Sjogren Syndrome'. Otherwise the patient will be classified as secondary Sjögren's syndrome                |
| Conversion of Time Intervals  | If a time interval was calculated in minutes, hours or days and needs to be converted into months or year the following conversion factors will be used:
• 1 hour = 60 minutes
• 1 day = 24 hours
• 1 week = 7 days
• 1 month = 30.4375 days
• 1 year = 365.25 days |
| General rule  | For calculation of a time interval, in case time is available, it is considered in the formula. Time intervals will be expressed in hours in if less than 24 hours and days if more than 24 hours.   |

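### SAP 9.3 multiplies artificial-tear use in drops/day by 100, and Table 3 limits the treatment-period count to the eligible eye but names no eye for follow-up

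*SAP*

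**What the plan says.** Artificial-tear use during treatment and during follow-up are exploratory endpoints in Protocol 7.1.3 and SAP 3.2.3, both in drops per day. SAP 9.3 repeats the unit: "The use (n° drops/day) of preservative free artificial tears will be summarized with descriptive statistics by treatment group and overall, by study period". It also asks for a figure over both periods combined. It then gives two formulas, one per period. Each divides the number of drops by the number of days and multiplies by 100. There is no formula for the combined figure.

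SAP Table 3 defines the components:

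- Treatment-period drops: "Sum of Morning/Afternoon/Evening Number of drops taken for eligible eye between Randomization visit date and End of Treatment date".
- Follow-up drops: "Sum of Morning/Afternoon/Evening Number of drops taken after End of Treatment date".
- Treatment-period days: "End of Treatment date – Randomization date + 1".
- Follow-up days: "Last follow-up available visit* date – End of Treatment date + 1", where the visit must have an assessment of tear use.

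Both drop counts come from the same eCRF form. Protocol 5.6 has the tears instilled in both eyes. Under Protocol 3.3 the follow-up diary is kept by eye: the patient "must document in the patient's diary the number of additional drops administered for each eye". SAP 7.9, which lists the changes from the protocol, mentions neither the factor 100 nor a difference in eye rule.

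**The concern.** There are two separate problems.

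First, drops divided by days is already drops per day. A factor of 100 belongs to a percentage such as the compliance formula in SAP 9.1, just before it. Applied here, it produces numbers that do not carry the stated unit.

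Second, adjacent rows of one table count different things on their face. The treatment row is one eye. The follow-up row names no eye, and counts for both eyes can be available. If both are summed, the two periods are on different scales, and any figure pooled across them mixes one-eye and two-eye counts.

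At stake are the reported level of two named endpoints (Tables 14.3.2.3.1 and 14.3.2.3.2, Listing 16.2.5.3), the descriptive comparison of the two periods, and the overall figure.

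**Working it through.** The documents give no numerical result for tear use, so there is no figure to reproduce. The check applies the SAP rules to a patient with known use.

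**Inputs.** Assumed: *x* drops per day in each eye, equal in both eyes and in both periods; randomization on day 1. From the visit schedule: end of treatment on day 28; last visit *L* on day 84, 112 or 168.

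**Days under Table 3.**
- Treatment: 28 − 1 + 1 = 28.
- Follow-up: *L* − 28 + 1 = 57, 85 or 141.

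**Factor 100, treatment period.** The eligible eye receives 28*x* drops. SAP 9.3 gives 28*x* / 28 × 100 = 100*x*. For *x* = 3 the table would show 300 where the use is 3 drops/day.

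**Eye rule, with the factor 100 removed.** Drops after day 28 fall on *L* − 28 days.
- Follow-up, both eyes summed: 2*x*(*L* − 28) / (*L* − 28 + 1).
- Overall, pooled (my assumption, since the SAP has no formula): [28*x* + 2*x*(*L* − 28)] / *L*.

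| Last visit | Follow-up, both eyes | Overall, mixed eyes |
|---|---|---|
| Day 84 | 112*x*/57 = 1.96*x* | 140*x*/84 = 1.67*x* |
| Day 112 | 168*x*/85 = 1.98*x* | 196*x*/112 = 1.75*x* |
| Day 168 | 280*x*/141 = 1.99*x* | 308*x*/168 = 1.83*x* |

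The per-eye value is *x* in every cell. With *x* = 3 and *L* = 168, follow-up is 840/141 = 5.96 drops/day, or 595.7 with the factor 100 left in.

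**Between-arm ratios.** The factor 100 cancels. Within follow-up, the factor 2 cancels if patients use both eyes equally. In a pooled figure it does not cancel in general, because follow-up drops carry double weight. Illustration with assumed use and *L* = 168: arm A uses 1 drop per eye per day in treatment and 3 in follow-up; arm B uses 3 and 3.
- Eligible eye only: (28 + 420) / (84 + 420) = 448/504 = 0.89.
- Mixed count: (28 + 840) / (84 + 840) = 868/924 = 0.94.

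**Day count.** The follow-up numerator starts after End of Treatment, but the +1 puts the End of Treatment day in the denominator. With the eligible eye only, follow-up reads 56/57 = 0.98 of the true value at day 84 and 140/141 = 0.99 at day 168, an effect under 2%.

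**The case against.** The strongest reply is that neither problem would survive programming or do harm. A table showing 300 drops per day would be noticed and can be rescaled without new data. For the eye rule, the neighbouring row names the eligible eye, both rows use the same form, and SAP 7.1 says some endpoints will be analysed on the eligible eye when applicable. The likely intention is one eye throughout. The endpoints are exploratory, the summaries are descriptive, and the tables are not among the key first results.

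Much of this stands. The doubling is conditional: it happens only if someone sums both eyes. But SAP 7.1 does not name this variable, so the choice stays open. Correcting the factor 100 silently would depart from the written plan, which says deviations are to be documented in the CSR. Nor can the factor be explained by the word proportion in the treatment-period endpoint: drops over days is not a proportion, and the follow-up endpoint, which is a frequency only, has the same factor.

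A reader might also infer that the eye mismatch would create a false rise in tear use from treatment to follow-up. The documents do not support putting it that way. Under Protocol 5.6 tears are used only if needed during treatment and three times daily in the eight weeks after it, so a rise is expected with correct formulas. No test of treatment against follow-up is planned. The mismatch could exaggerate a rise; it would not be its only source.

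**Conclusion.** The point holds in two parts of different certainty. The factor 100 is an error in the written formulas: values programmed as written and labelled drops/day are exactly 100 times too high. The eye rule is an inconsistency whose effect depends on how it is programmed. If both eyes are summed and used equally, follow-up use reads 1.96 to 1.99 times the per-eye value.

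A reader might infer that overall use is doubled as well. That goes too far. The SAP defines no overall formula, and under simple pooling with equal use in both periods the inflation is 1.67 to 1.83 times. It reaches 2 only if no tears are used during treatment.

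The consequence is limited to exploratory, descriptive output. The co-primary tests do not use these quantities. The factor 100 does not alter any between-arm ratio, and the eye rule does not alter one within a period if both eyes are used equally. The plan should still be corrected, because it is wrong as written and the correction costs nothing.

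**What to change.** - In SAP 9.3, delete the multiplication by 100 from both artificial-tear formulas.
- In SAP Table 3, add the eligible-eye restriction to the follow-up drop count, so that it matches the treatment row.
- Define overall use as total eligible-eye drops over both periods divided by total days.
- Start the follow-up day count on the day after End of Treatment (last available visit date minus End of Treatment date, without the +1), so that numerator and denominator cover the same days.

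With these changes the patient using 3 drops per eye per day to day 168 gives 84/28 = 3.0 in treatment, 420/140 = 3.0 in follow-up and 504/168 = 3.0 overall.

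The cost is a few SAP wording edits, best made before unblinding. No additional data or patients are needed.

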## 9.4.6. Subgroup analysis

Subgroup analyses of primary and secondary endpoints will be performed on the following subgroups of baseline characteristics:

- Age class (*Median*, *Median*),
- Race,
- Gender,
- Ethnicity,
- Sjögren's syndrome (primary, secondary).

Statistical details and potential new subgroups definitions will be reported in the SAP.

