#### For a primary Sjögren's syndrome diagnosis:

- Any 4 of the 6 criteria, must include either item IV (Histopathology) or VI (Autoantibodies)
- Any 3 of the 4 objective criteria (III, IV, V, VI)

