#### For a secondary Sjögren's syndrome diagnosis:

• In patients with another well-defined major connective tissue disease, the presence of one symptom (I or II) plus 2 of the 3 objective criteria (III, IV and V) is indicative of secondary SS.

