#### 7.5 Sub-group analyses

Subgroup analyses of primary and secondary endpoints will be performed on the following subgroups of baseline characteristics:

- Age class (*Median*, *Median*).
- Race.
- Ethnicity.
- Gender.

Within each subgroup level, descriptive in nature analyses will be performed on:

- Schirmer I test.
- SANDE global, frequency and severity scores.
- NEI scale.

- TFBUT.
- IDEEL questionnaire.

at each available timepoints by means of descriptive statistics.

In case of continuous measures, analyses will be provided for baseline visit, each post-baseline visit, and their change from baseline. Comparisons between treatments will be performed using twosample t-test (assuming unequal variances) or, if the required assumptions are not met, the twosample Mann–Whitney U test will be used. Assumption of normal distribution of endpoints for continuous data will be assessed by a visual inspection of distribution.

In case of categorical variables, the Fisher's Exact test will be provided in addition to summary description.

Statistical tests for interaction (between subgroup variable and treatment arm) will be performed before investigating further subgroups: analyses of primary endpoints will be performed using regression models including treatment, subgroup variable and their interaction as covariate. If the interaction between subgroup variable and treatment arm is statistically significant at 15% nominal level in at least one regression model, then subgroup analysis will be performed.

Variables that may be evaluated after test for interaction are:

- Region (Europe, US),
- Sjögren's syndrome (primary, secondary), where "primary" is defined as a confirmed diagnosis of Sjögren's syndrome while "secondary" as other autoimmune disease known to induce Sjögren's Dry Eye Disease,
- Medical history,
- Concomitant medication.

Subgroup levels may be pooled to have an adequate number of subjects per strata to perform the analysis. Decision on pooling will be taken during the Blind Data Review Meeting (BDRM) before data base lock.

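### SAP Table 3 assigns primary or secondary Sjögren's from ocular history alone, which conflicts with SAP 7.5 and with Appendix 3 and can mislabel patients in a protocol-planned subgroup

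*SAP*

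**What the plan says.** Protocol 9.4.6 plans subgroup analyses of the primary and secondary endpoints by "Sjögren's syndrome (primary, secondary") and adds: "Statistical details and potential new subgroups definitions will be reported in the SAP".

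The terms then have three definitions:

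- **Protocol Appendix 3.** Primary: "Any 4 of the 6 criteria, must include either item IV (Histopathology) or VI (Autoantibodies"), or three of the four objective criteria. Secondary: "In patients with another well-defined major connective tissue disease, the presence of one symptom (I or II) plus 2 of the 3 objective criteria".
- **SAP 7.5.** Primary "is defined as a confirmed diagnosis of Sjögren's syndrome while" secondary is another autoimmune disease that induces Sjögren's dry eye disease.
- **SAP 12.1, Table 3.** Primary if the patient had "any previous and/or concomitant ocular with diagnosis='Sjogren Syndrome'". "Otherwise the patient will be classified as secondary" Sjögren's.

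The Schedule of Evaluations collects both ocular and systemic medical history. SAP 8.5 codes diseases in MedDRA and tabulates them as ophthalmic or non-ophthalmic. SAP 7.9, which lists changes from the protocol, does not mention this variable.

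**The concern.** Table 3 is the rule that will be programmed, and it matches neither of the other two definitions. It does not read systemic history, so it is narrower than SAP 7.5. It never looks for a second autoimmune or connective tissue disease, which is the feature that marks secondary in Appendix 3. Its secondary class needs no positive evidence.

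What is at stake is the interpretation of one subgroup. The variable feeds the treatment-by-Sjögren's interaction tables for both co-primary endpoints (SAP Tables 14.2.6.1.2 and 14.2.6.2.2). It also feeds the 15% interaction test that decides, under SAP 7.5, whether this subgroup is analysed further. If labels are wrong, effects are credited to the wrong disease type and a real difference between types is harder to see.

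**Working it through.** The plan gives no figure for this subgroup, so there is none to reproduce. The check is to trace patient types through the three definitions. (CTD = another major connective tissue disease.)

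| Recorded history | Table 3 | SAP 7.5 | Appendix 3 |
|---|---|---|---|
| A. Sjögren's in ocular history, no CTD | primary | primary | primary |
| B. Sjögren's in systemic history only, no CTD | **secondary** | primary | primary |
| C. Sjögren's in ocular history, plus CTD | **primary** | primary if read literally; precedence not stated | secondary |
| D. CTD, no Sjögren's entry | secondary | secondary | secondary if its criteria are met |
| E. Neither recorded | **secondary** | neither | neither |

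The Appendix 3 column assumes that the patient meets the relevant criteria. Appendix 3 does not say outright that primary excludes another connective tissue disease; that follows from its separate secondary category.

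- Row B is wrong under SAP 7.5 and under Appendix 3. It arises only if the eCRF lets a site enter Sjögren's solely as systemic history.
- Row C is wrong under Appendix 3 only. Inclusion criterion 2 admits such patients, since a Sjögren's diagnosis qualifies with or without another disease.
- Row E puts a patient with no relevant entry into a disease class.

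**Size, by assumption.** If misclassification is unrelated to outcome, the observed contrast between subgroups is the true contrast times k = PPV + NPV − 1. PPV and NPV are the shares of labelled-primary and labelled-secondary patients whose label is right. With equal true groups and error rate e each way, PPV = NPV = 1 − e, so k = 1 − 2e:

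- e = 15%: k = 0.85 + 0.85 − 1 = 0.70
- e = 30%: k = 0.70 + 0.70 − 1 = 0.40

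**The 15% test, SANDE model only.** N = 72 and SD = 12 come from SAP section 5. A true interaction of 10 points and equal subgroups of 36 are assumptions.

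SE of the interaction = 12 × √(4/36 + 4/36) = 5.66. The two-sided 15% critical value is 1.44. Power = Φ(10k/5.66 − 1.44) + Φ(−10k/5.66 − 1.44).

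| Error each way | k | Power at 15% |
|---|---|---|
| 0 | 1.00 | 63% |
| 10% | 0.80 | 49% |
| 20% | 0.60 | 36% |
| 30% | 0.40 | 25% |

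If 70% of patients are truly primary, the four power values are 57%, 43%, 31% and 22%. The test also passes if the Schirmer model is significant, so these figures cover only one of its two routes.

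**The case against.** The strongest reply is that Appendix 3 may not govern this variable. Neither inclusion criterion 2 nor Protocol 9.4.6 cites it, and 9.4.6 leaves statistical details to the SAP. SAP 7.5 then gives a study definition that mirrors the two arms of criterion 2. On that definition a patient with Sjögren's plus another disease is arguably primary by design, so row C is a dispute about which definition applies and not a proven coding error. This stands, but it does not rescue Table 3. The ocular restriction departs from SAP 7.5 itself, and SAP 7.5 does not say how to class a patient who has both conditions.

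The second reply is that row B depends on the eCRF, which is not among the documents. If the form always files Sjögren's under ocular history, row B disappears. That also stands.

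The third is that the consequence is small. The interaction tables for both co-primary endpoints are listed without condition, so the interaction is reported whatever the 15% test shows. Only the follow-up subgroup tables can be withheld. Even with perfect labels, the illustration gives the SANDE test only 63% power.

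**Conclusion.** The point holds as an inconsistency between definitions that allows wrong labels. Table 3 conflicts with SAP 7.5 on where the diagnosis is looked for, and with Appendix 3 on what separates the two types.

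A reader might infer that patients are in fact misclassified in both directions. The documents do not support that. One direction needs an eCRF that accepts systemic-only entries, and the other needs Appendix 3 to be the governing definition. Nor can the number affected be computed, because neither recording practice nor the share of patients with another connective tissue disease is given.

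The shrinkage factors of 0.70 and 0.40 rest on assumed error rates, equal groups, and errors unrelated to outcome. If mislabelled patients respond differently from the rest of their true class, the bias need not be toward zero.

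The effect is confined to the subgroup and interaction analyses. The co-primary tests, the key secondary sequence and the sample size do not use this variable. The priority is low, but the correction is cheap and should come before unblinding, because a later change would look post hoc.

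**What to change.** Replace the Table 3 rule with one derived from coded ocular and systemic history together:

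- **Primary:** Sjögren's syndrome recorded in either history, with no other major connective tissue or autoimmune disease.
- **Secondary:** another such disease, with Sjögren's syndrome or Sjögren's dry eye disease. This covers patients admitted through the other-autoimmune-disease arm of criterion 2.
- **Unclassifiable:** neither recorded.

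Fix the list of qualifying coded terms while blind, and confirm each patient's class from a listing at the blind data review. Put the same definition in SAP 7.5 and Table 3, state how it relates to Appendix 3, and list the change in SAP 7.9.

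The SAP should not claim to apply the full Appendix 3 criteria. Those use lip biopsy, autoantibodies and salivary tests, and none of these is in the Schedule of Evaluations.

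The cost is one derivation rule, one blinded listing and a short SAP amendment. Both histories are already scheduled for collection and coding, so no new assessment is needed.

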# **12.2 SANDE derivation**

The SANDE questionnaire is comprised of two questions:

- How often do your eyes feel dry and/or irritated?
- How severe you feel your symptoms of dryness and/or irritation are?

This questionnaire uses a 100 mm horizontal line for each question to assess ocular discomfort and/or dryness experienced by the patients. In the SANDE questionnaire, frequency of symptoms ranges from "rarely" to "all of the time" and the severity of symptoms ranges from "very mild" to "very severe". Patients are asked to place a mark on the two given lines based on the extent of their symptoms.

The locations of the marks made by the patients on the 100 mm horizontal lines will be measured in mm from left to right and recorded as frequency and severity score, respectively.

The global SANDE score will be calculated by multiplying the frequency score by the severity score and obtaining the square root.

